5.1 Inclusion Criteria

Patients must meet all of the Inclusion Criteria in order to participate in the study

- Subjects who are considered to be operable and high risk for surgical valve replacement: 8 ≤ STS Score ≤ 15 or 15 ≤ Logistic EuroSCORE ≤ 40. If STS score is below 8 and/or Logistic EuroSCORE is below 15, patients should have other clinical or anatomical risk factors that would be considered high risk for surgery and documented by the heart team
- Severe symptomatic aortic stenosis requiring aortic valve replacement characterized by one or more of the following within 60 days prior to the index procedure: AVA < 0.8 cm², Indexed AVA <0.5 cm²/m², mean gradient > 40mmHg, or peak aortic jet velocity > 4.0m/sec. [41]
- 3. NYHA Functional Class II or greater.
- 4. The study patient or the study patient's legal representative has been informed of the nature of the study, agrees to its provisions and has provided written informed consent as approved by the EC of the respective clinical site.
- 5. The study patient agrees to comply with all required post-procedure follow-up visits.
- 6. Native aortic valve annulus area between 314 mm² 660 mm² as measured by CT.
- 7. Native aortic annulus diameter between 20 mm 29 mm as measured by CT.

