5.2 Exclusion Criteria

Patients must not meet any of the Exclusion Criteria in order participate in the study

- Evidence of an acute myocardial infarction ≤ 1 month (30 days) before the intended treatment [(defined as: Q wave MI, or non-Q wave MI with total CK elevation of CK-MB ≥ twice normal in the presence of MB elevation and/or troponin level elevation (WHO definition)].
- 2. Aortic valve is a congenital unicuspid or is non-calcified.
- 3. Aortic valve is bicuspid and the patient is less than 60 years old, or the aortic valve is bicuspid with no raphe (Sievers classification type 0) [42]
- 4. Anomalous coronary artery that would interfere with proper placement of the valve.
- 5. Mixed aortic valve disease (aortic stenosis and aortic regurgitation with predominant aortic regurgitation >3+).

- 6. Pre-existing mechanical or bioprosthetic valve in any position.
- 7. Any therapeutic invasive cardiac procedure resulting in a permanent implant that is performed within 30 days of the index procedure. Implantation of a permanent pacemaker or ICD is not considered exclusion criteria.
- 8. Any patient with a balloon valvuloplasty (BAV) within 30 days of the procedure (unless BAV is a bridge to procedure after a qualifying echocardiogram).
- Leukopenia (WBC < 3000 cell/mL), acute anemia (Hgb < 9 g/dL), Thrombocytopenia (Plt < 50,000 cell/mL).
- 10. Renal insufficiency (creatinine > 3.0 mg/dL) and/or renal replacement therapy at the time of screening.
- 11. Untreated clinically significant coronary artery disease requiring revascularization.
- 12. Emergency interventional/surgical procedures within one month (30 days) prior to the TAVI procedure.
- 13. Hypertrophic cardiomyopathy with or without obstruction (HOCM).
- 14. Severe ventricular dysfunction with LVEF < 20%.
- 15. Echocardiographic evidence of intracardiac mass, thrombus or vegetation.
- 16. Active upper GI bleeding within 3 months (90 days) prior to procedure.
- 17. A known contraindication or hypersensitivity to all anticoagulation regimens, or inability to be anticoagulated for the study procedure.
- 18. Stroke or transient ischemic attack (TIA) within 3 months (90 days) of the procedure.
- 19. Estimated life expectancy < 12 months (365 days) due to carcinomas, chronic liver disease, chronic renal disease or chronic end stage pulmonary disease.

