6.3.2 Patient Screening and Enrolment

The study site shall have a committed Heart Team involved in the screening process. The Heart Team will include at least two cardiac surgeon, one interventional cardiologist, one radiologist, and one anesthesiologist but could also include (without being limited to) the following specialties:

- Echocardiography
- Gerontology

The screening of patients in cardiovascular and cardiac surgery departments will be conducted by one or more delegated study team members. The study team will be responsible for ensuring and reporting study patient screening for study eligibility. Cumulative screening and enrollment logs will be maintained by study sites. Reasons for screen failures will be documented in study logs.

To accommodate the implant procedure learning curve, a roll-in strategy will be available. Each study site will be allowed up to two roll-in patients. Edwards Lifesciences will document if the

patient is a roll-in patient before the implant procedure begins. Roll-in patients will complete all study visits and procedures, and not be counted toward the 60 implanted patients.

In addition, the Heart Team will be required to assess all patients for study inclusion to ensure compliance to surgical risk criteria, screening procedures to assess valve size and delivery method, and other inclusion/exclusion criteria. After heart team identifies a patient, the Sponsor will review and confirm eligibility during the case review process.

All patients who sign a study informed consent will be entered into the database. Subjects will be included in analysis of the trial if an Edwards' investigational device is inserted into the patient. Only patients that leave the procedure room with a SAPIEN XT THV in place will be counted toward the 60 implanted patients.

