6.3.3.1 Screening

The following screening data will be collected for all study patients to assess eligibility as per standard of care:

- Operability Risk Assessment
- Medical history, pertinent physical examination [include blood pressure, height, weight and all major systems findings]
- NYHA functional classification
- CSS Angina classification
- Risk assessment (STS Risk Score, Logistic EuroSCORE, and EuroSCORE II)

Non-Invasive Studies (must be completed within 60 days before procedure date)

• Comprehensive transthoracic echocardiogram (TTE) (transesophageal echocardiogram (TEE) may be used as an alternative)

Invasive Studies (must be completed before the procedure date)

- Cardiac and abdominal CT angiogram with visualization of the aortic arch, both iliac and femoral arteries to the aorta. In the situation where patients have compromised renal function that precludes the use of contrast agents, MR imaging may be used as an alternative to CT (≤180 days before procedure)
- Left heart catheterization to assess the severity of aortic stenosis and severity of coronary artery disease (≤180 days before procedure)

If any assessments need to be completed or repeated outside of standard of care, a patient will need to sign a Patient Informed Consent prior to completing assessments.

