11.3 Analysis Sets

- As Treated (AT) Population: all patients that were enrolled in the trial for whom the SAPIEN XT valve implant procedure was begun, defined as the time in which the first Edwards' investigational device is inserted into the patient.
- *Valve Implant (VI) Population:* all AT patient who received and retained the SAPIEN XT valve upon leaving the procedure room

All patients documented as part of the roll-in patient strategy will not be included in analysis population and evaluated separately.

The primary and secondary endpoints will be reported based on the AT Population. AT patients that did not receive the SAPIEN XT valve will be censored at 30 days or at resolution of any AE.

Descriptive and summary statistical analysis will be performed on all endpoints. Patient listings for adverse events, deaths, and reinterventions will include all enrolled patients.

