13.2.2 Deviations from Protocol

The investigator will not deviate from the protocol without the prior written approval of Edwards Lifesciences except in medical emergencies or in unforeseen, isolated instances where minor changes are made that will not increase the patient's risk or affect the validity of the trial. In medical emergencies, prior approval for protocol deviations will not be required, but the Edwards Lifesciences clinical research personnel must be notified within 24 hours of the incident.

All protocol deviations need to be recorded in the respective section of the eCRF and reported according national and ethics committee requirements. Periodic monitoring of protocol compliance will be performed for each site. The sponsor maintains the right to place a moratorium on enrollment in sites deemed to have excessive protocol compliance issues. A major protocol violation is the instance where a deviation significantly affects the integrity of the study and guidelines for Good Clinical Practice, such as when there is failure to obtain informed consent or violation of inclusion/exclusion criteria. In cases of major protocol violation, the principal investigator is required to make a written statement attesting to retraining or other action(s) to be taken at his/her site to avoid such violations in the future.

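### Does inclusion criterion 1 need rewording because its two sentences can disagree when one surgical risk score is low and the other is in range?

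*Combined protocol and SAP*

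**What the plan says.** Item 1 of Section 5.1 restricts entry to patients judged operable and at high risk for surgical valve replacement. Its first sentence gives the score windows: "8 ≤ STS Score ≤ 15 or 15 ≤ Logistic EuroSCORE ≤ 40". Its second sentence reads: "If STS score is below 8 and/or Logistic EuroSCORE is below 15, patients should have other clinical or anatomical risk factors", with those factors to be such as would be regarded as high surgical risk and documented by the heart team. The Synopsis carries the same two sentences. The line heading Section 5.1 states: "Patients must meet all of the Inclusion Criteria in order to participate in the study".

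Four other places bear on the point:

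- Section 6.3.3.1 lists "Risk assessment (STS Risk Score, Logistic EuroSCORE, and EuroSCORE II") among the data collected for all study patients.
- Section 6.3.2 requires the Heart Team to assess every patient against the surgical risk criteria, and then: "After heart team identifies a patient, the Sponsor will review and confirm eligibility during the case review process".
- Section 11.3 states: "The primary and secondary endpoints will be reported based on the AT Population". Membership of that set turns on whether an investigational device was inserted.
- Section 13.2.2 defines a major protocol violation as a deviation that significantly harms the integrity of the study and GCP, and gives examples: "such as when there is failure to obtain informed consent or violation of inclusion/exclusion criteria".

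**The concern.** The first sentence joins the two scores by *or*; the second uses *and/or*. Take a patient with STS 10 and Logistic EuroSCORE 12, or STS 7 and Logistic EuroSCORE 30, and no other documented risk factor. The first sentence lets that patient in. The second, if it binds, does not. The header of Section 5.1 is mandatory, whereas the second sentence says *should*, so the text does not show whether the second sentence is a condition or advice.

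If this mattered, it would do so in two ways. The same enrolment could be called compliant by one reader and a major violation by another. And in a single-arm study, the entry criteria define the high-risk population that the 30-day mortality figure describes, so an unclear criterion could blur what the estimate refers to.

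**Working it through.** There is no stated figure to reproduce; the check is one of logic.

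**Inputs.** From Section 5.1, item 1: STS window 8 to 15, Logistic EuroSCORE window 15 to 40, low-score triggers STS below 8 and Logistic EuroSCORE below 15.

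**Rules.** Let S1 be true if STS is 8 to 15 or Logistic EuroSCORE is 15 to 40. Let L be true if STS is below 8 or Logistic EuroSCORE is below 15. Let F be true if other risk factors are documented. Three readings are tenable:

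- Reading A (factors are an alternative route): eligible if S1, or if L and F.
- Reading B (the second sentence qualifies the first): if L, eligible only with F; otherwise S1 decides.
- Reading C: as B, except that a patient with one score low and the other above its cap is out, because S1 is not met.

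**Results**, using STS 7 / 10 / 20 and Logistic EuroSCORE 12 / 30 / 55 for low / in range / above cap:

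| STS | Logistic EuroSCORE | A | B | C |
|---|---|---|---|---|
| 7 | 12 | with F | with F | with F |
| 7 | 30 | in | with F | with F |
| 7 | 55 | with F | with F | out |
| 10 | 12 | in | with F | with F |
| 10 | 30 | in | in | in |
| 10 | 55 | in | in | in |
| 20 | 12 | with F | with F | out |
| 20 | 30 | in | in | in |
| 20 | 55 | out | out | out |

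A and B differ in 2 of 9 rows, (7, 30) and (10, 12), and there only for patients without F. Once C is allowed, (7, 55) and (20, 12) also differ, giving 4 of 9; in those two rows the affected patient is the one with F. The count therefore depends on which readings are admitted. It also weights every row equally, and the documents give no joint distribution of the two scores. It shows where the text is open, not how many patients are involved.

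**Who settles an open row.** Section 6.3.2 puts each patient through the Heart Team and then through the sponsor. Section 12.6 has the sponsor evaluate departures from the protocol. The party that confirms eligibility also judges deviations, so one reading can be held across the three sites.

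**What reaches the analysis.**

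- Sample size: Section 11.1 sets 50 to 60 patients by regulatory agreement. No score enters it.
- Analysis sets: Section 11.3 defines them by device insertion and by retention of the valve on leaving the procedure room. Eligibility does not enter.
- Primary analysis: Section 11.5 specifies a Kaplan-Meier estimate of 30-day mortality with Greenwood confidence limits. The computation is the same under A, B or C, and Section 11 sets no performance goal that a slightly different case mix could tip.
- Description: Section 11.5 tabulates clinically relevant baseline variables. With both scores recorded for each patient, the enrolled risk profile can be shown in full.

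**The case for a change.** The best case for a change is that the conflict can be verified from the text alone. *And/or* expressly covers a single low score, the Synopsis repeats the wording and so cannot resolve it, and the Heart Team, the sponsor and the monitors all work from the same unclear sentence. Section 13.2.2 names breach of the entry criteria as an example of a major violation, which obliges the principal investigator to make a written statement. Rewording would take a line in two places.

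The ambiguity stands. So does the related gap on whether documented factors admit a patient with one score low and the other above its cap.

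The consequences are weaker than they look. On ordinary construction, a later and more specific sentence qualifies an earlier general one. That gives Reading B, a coherent rule in which the *or* of the first sentence still does work at (10, 55) and (20, 30). Reading A remains possible, but the text is loose rather than self-defeating. The major-violation label needs significant harm to the integrity of the study; a patient whom the Heart Team assessed as high risk and the sponsor confirmed is hard to place there. The population argument is also limited: each reading admits only patients judged operable and high risk, and differs in whether one in-range score is enough without further documentation or, under C, in how a score above its cap is treated.

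**Conclusion.** No change to the plan is called for. This is a drafting ambiguity that the people running the trial can settle case by case through a review step the protocol already requires. Its effect on the sample size, the analysis sets and the computation of the primary endpoint is nil. Its effect on who is enrolled is confined to patients whose two scores disagree; their number cannot be derived, and the ceiling is 60 counted implants plus up to two roll-in patients per site, who are evaluated separately. Rewording would bring no demonstrable gain in what the study can conclude, and the choice of rule would in any case rest with the sponsor and the heart team.

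This rests on three assumptions: that the sponsor's case review applies one reading throughout, that both scores and any additional risk factors are recorded as the protocol requires, and that the baseline scores are tabulated with the results. If the first failed, the result would be a somewhat more mixed risk profile, which the recorded scores would show.

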5.2 Exclusion Criteria

Patients must not meet any of the Exclusion Criteria in order participate in the study

- Evidence of an acute myocardial infarction ≤ 1 month (30 days) before the intended treatment [(defined as: Q wave MI, or non-Q wave MI with total CK elevation of CK-MB ≥ twice normal in the presence of MB elevation and/or troponin level elevation (WHO definition)].
- 2. Aortic valve is a congenital unicuspid or is non-calcified.
- 3. Aortic valve is bicuspid and the patient is less than 60 years old, or the aortic valve is bicuspid with no raphe (Sievers classification type 0) [42]
- 4. Anomalous coronary artery that would interfere with proper placement of the valve.
- 5. Mixed aortic valve disease (aortic stenosis and aortic regurgitation with predominant aortic regurgitation >3+).

- 6. Pre-existing mechanical or bioprosthetic valve in any position.
- 7. Any therapeutic invasive cardiac procedure resulting in a permanent implant that is performed within 30 days of the index procedure. Implantation of a permanent pacemaker or ICD is not considered exclusion criteria.
- 8. Any patient with a balloon valvuloplasty (BAV) within 30 days of the procedure (unless BAV is a bridge to procedure after a qualifying echocardiogram).
- Leukopenia (WBC < 3000 cell/mL), acute anemia (Hgb < 9 g/dL), Thrombocytopenia (Plt < 50,000 cell/mL).
- 10. Renal insufficiency (creatinine > 3.0 mg/dL) and/or renal replacement therapy at the time of screening.
- 11. Untreated clinically significant coronary artery disease requiring revascularization.
- 12. Emergency interventional/surgical procedures within one month (30 days) prior to the TAVI procedure.
- 13. Hypertrophic cardiomyopathy with or without obstruction (HOCM).
- 14. Severe ventricular dysfunction with LVEF < 20%.
- 15. Echocardiographic evidence of intracardiac mass, thrombus or vegetation.
- 16. Active upper GI bleeding within 3 months (90 days) prior to procedure.
- 17. A known contraindication or hypersensitivity to all anticoagulation regimens, or inability to be anticoagulated for the study procedure.
- 18. Stroke or transient ischemic attack (TIA) within 3 months (90 days) of the procedure.
- 19. Estimated life expectancy < 12 months (365 days) due to carcinomas, chronic liver disease, chronic renal disease or chronic end stage pulmonary disease.
- 20. Significant aortic disease, including marked tortuosity (hyperacute bend), aortic arch atheroma [especially if thick (> 5 mm), protruding or ulcerated] or narrowing (especially with calcification and surface irregularities) of the abdominal or thoracic aorta, severe "unfolding" and tortuosity of the thoracic aorta.
- 21. Iliofemoral vessel characteristics that would preclude safe placement of the introducer sheath.
- 22. Currently participating in an investigational drug or another device study. Note: Trials requiring extended follow-up for products that were investigational, but have since become commercially available, are not considered investigational trials.
- 23. Active bacterial endocarditis within 6 months (180 days) of procedure, with our without treatment.

6. Investigation Plan

6.1 Study Design

This is a prospective, single-arm, multi-center study to assess the safety and effectiveness of the SAPIEN XT THV. Up to 60 patients will be enrolled and implanted with the device at three sites in China over an estimated six month enrolment period with a follow-up period to 5 years.

An Echocardiography Core Lab will be established for standardizing echocardiographic secondary endpoints. A Medical Reviewer will review all endpoint-related adverse events.

6.2 Study Compliance and Regulations

The SAPIEN XT THV System is not commercially available in China. The clinical investigation shall be conducted in accordance with the ethical principles that have their origin in the Declaration of Helsinki (as updated in Fortaleza Brazil in 2013) and in compliance with China's Good Clinical Practice (GCP) for Medical Devices and any national regulations. The clinical investigation plan and Patient Informed Consent form used to study the SAPIEN XT THV System must be reviewed and approved by the appropriate national authority and local or regional Ethics Committee (EC) where the clinical investigation is to be conducted before enrolment of patients may begin. Any additional requirements imposed by the EC or regulatory authority shall be followed.

Changes to the investigational plan that may increase the risk or present new risks to the patient must be approved in writing by Edwards Lifesciences and the EC before the change is implemented.

6.3 Study Procedures

6.3.1 Informed Consent

The Patient Informed Consent Form must be approved by Edwards Lifesciences and the site's EC.

The study investigator(s) and support staff will approach patients with symptomatic aortic stenosis to assess their interest in participating in the study. They will provide an overview of the study and device, including the background, benefits, risks, and study procedures. If patients are interested in participating in the study, then they will be provided with the full Patient Informed Consent Form document. Patients will be allowed to read the document in its entirety, and then delegated study personnel will answer all of their questions. If the patient is comfortable with proceeding, then they will be asked to sign and date the Patient Informed Consent Form. Informed consent must be obtained prior to the screening procedures or baseline tests that are specific to this study.

During the course of the study, if new information becomes available that can affect a patient's future health and medical care, then the information will be provided to the patient and the process documented. If relevant, all affected patients will be asked to confirm their continuing informed consent in writing.

All patients who sign a Patient Informed Consent Form should be entered in the database. Data should not be entered until a Patient Informed Consent Form is signed. Patients that are screened and do sign a Patient Informed Consent Form should be documented on the Screening Log.

6.3.2 Patient Screening and Enrolment

The study site shall have a committed Heart Team involved in the screening process. The Heart Team will include at least two cardiac surgeon, one interventional cardiologist, one radiologist, and one anesthesiologist but could also include (without being limited to) the following specialties:

- Echocardiography
- Gerontology

The screening of patients in cardiovascular and cardiac surgery departments will be conducted by one or more delegated study team members. The study team will be responsible for ensuring and reporting study patient screening for study eligibility. Cumulative screening and enrollment logs will be maintained by study sites. Reasons for screen failures will be documented in study logs.

To accommodate the implant procedure learning curve, a roll-in strategy will be available. Each study site will be allowed up to two roll-in patients. Edwards Lifesciences will document if the

patient is a roll-in patient before the implant procedure begins. Roll-in patients will complete all study visits and procedures, and not be counted toward the 60 implanted patients.

In addition, the Heart Team will be required to assess all patients for study inclusion to ensure compliance to surgical risk criteria, screening procedures to assess valve size and delivery method, and other inclusion/exclusion criteria. After heart team identifies a patient, the Sponsor will review and confirm eligibility during the case review process.

All patients who sign a study informed consent will be entered into the database. Subjects will be included in analysis of the trial if an Edwards' investigational device is inserted into the patient. Only patients that leave the procedure room with a SAPIEN XT THV in place will be counted toward the 60 implanted patients.

